3.5 Trial Setting and Duration

This multicentre trial will be conducted in approximately 20 NHS trusts across the UK. It is anticipated that participants will be recruited from a number of secondary care settings including but not limited to, falls clinics, day hospitals, geriatric medicine clinics and movement disorder clinics.

During the 10-month pilot phase we intend to open 14 centres. Following the internal pilot an additional six sites will be opened to reach a total randomisation target of 366 patients over the 30-month recruitment period (20 sites in total). Participants will be followed up for a total of 12 months following randomisation.

4. Trial Participants

4.1 Overall Description of Trial Participants

Adults aged 18 years or over with symptomatic OH will be screened for eligibility. Eligibility must be confirmed by a medically qualified doctor using the eligibility confirmation document and documented in the participant's medical notes. Only personnel formally delegated by the Principal Investigator at each site to assess eligibility may perform this task.

4.2 Inclusion Criteria

- Adults aged 18 years and over
- A clinical diagnosis of symptomatic OH which is either:

1. Clinically significant where you would wish to start treatment quickly without a trial of lifestyle modification OR
 2. Refractory to an adequate period of lifestyle modification (to be judged clinically)
- A drop in systolic blood pressure of ≥ 20 mmHg and/or a drop in diastolic blood pressure of ≥ 10 mmHg, within three-minutes of standing upright from a supine position (or on tilt-testing) which has been obtained at baseline.
 - A score of ≥ 2 on the OHQ
 - Willing and able to provide informed consent prior to any trial procedures taking place.

4.3 Exclusion Criteria

- OH secondary to acute or reversible causes (e.g. haemorrhage, sepsis)
- Use of fludrocortisone or midodrine within the last six months
- Terminal illness or life expectancy < 12 months
- Supine hypertension (where the risks of treatment outweigh the benefits) at baseline
- A known allergy to study medication
- A known contra-indication to fludrocortisone or midodrine which outweighs the potential clinical benefit (i.e. if in usual clinical care the clinician and participant feel the risks outweigh the benefits, they would be excluded)
- Current or planned pregnancy during the trial period, or breast feeding (if randomised to either pharmacological arm the participant, if female and of child-bearing potential, must have a negative pregnancy test [urine beta-human chorionic gonadotropin (β -hCG)] and are required to use a highly effective contraceptive method during the trial).
- Inability to communicate in English
- Inability to comply with the study procedures as specified in the schedule of events.
- Currently taking part in another clinical trial that would interfere with the outcomes of CONFORM-OH (site team to check with the CI and Trial Management Group if in doubt)

NB: Enrolling a patient onto the trial who does not meet the inclusion/exclusion criteria is considered a protocol waiver and is in breach of Regulation 29 (SI 2004/1031) of the Medicines for Human Use (Clinical Trials) Regulations 2004. PROTOCOL WAIVERS ARE NOT PERMITTED.

5. Trial Procedures

5.1 Recruitment

5.1.1 Pre-screening, Screening and Eligibility Assessment

Adults attending routine clinic appointments (including face-to-face, telephone, video or other forms of consultation) at participating sites, should be pre-screened to confirm they have symptomatic OH requiring treatment. Pre-screening can also include reviewing local patient research participation databases, clinic lists and opportunistic screening. Information about the study may also be displayed on posters in the relevant clinical areas at participating sites so that potential participants will be able to approach staff for more information.

The initial approach will be made by the clinical team. The research team can only approach patients directly if they are imbedded within the clinical team, or permission has been obtained from the patient for them to carry out this activity.

Potential participants identified from pre-screening should be screened for eligibility into the trial using the patients' medical history. All patients screened for eligibility should be recorded on the screening log and assigned a screening identification number, irrespective of their participation in the trial; reasons for ineligibility and non-consent will be captured.

Following eligibility screening, patients that may be eligible will be provided with the Patient information leaflet (PIL) by the clinical team prior to their routine clinical appointment, along with a letter explaining that they may be eligible to take part in a research trial. During the clinical appointment the clinical team will discuss the study and confirm that the patient meets the eligibility criteria for consent.

If for any reason the patient did not receive the PIL in advance of their clinic appointment, the clinical team will inform the patient of the trial, ensure the patient is provided with a PIL, and request the patient's permission for a member of the clinical or research team to contact them to discuss the trial in more detail and answer any questions.

No research activity will take place prior to informed consent.

Re-screening is permitted if deemed necessary by the physician, and must be documented thoroughly and clearly at site, in the patient notes and on the eCRF. If re-screened participants will be given a new screening identification number.

5.1.2 Informed Consent

Potentially eligible patients will be provided with a PIL which will explain the exact nature of the study, the implications and constraints of the protocol and any risks involved in taking part. It will be clearly stated that the patient is free to withdraw from the study at any time for any reason without prejudice to future care, and with no obligation to give the reason for withdrawal. However, patients will be informed that we would like to know their reason for withdrawal, to assist with the identification of problems with the study and areas to improve. The study will be explained in more detail by a member of the clinical or research team and patients will be given the opportunity to ask any questions. If the research team provides study information, the treating clinician will first obtain permission from the patient for them to carry out this activity.

Patients who received the PIL prior to their clinic appointment, and would like to participate, can have their eligibility confirmed following full consent discussions between the patient and clinician, with consent obtained at the clinic appointment or remotely.

Patients who are provided with the PIL at the clinic appointment, will be given adequate time to consider participation, after which a member of the research team will contact them to provide the opportunity to ask questions and discuss the study. If the patient would like to participate, eligibility can be confirmed using the eligibility confirmation document and an appointment can be arranged for the consent form to be completed using one of the following methods:

1. Completion of the consent process at a routine face-to-face clinic visit, research clinic or home visit.
2. Remote completion of the consent process via videoconference. The consent form is provided in advance and is signed by the participant, witnessed by the consenting clinician using videoconference facilities. Additional identification questions should be asked, in line with local policy to confirm the identity of the patient prior to the consent form being signed.
3. Remote completion of the consent process via telephone. The consent form is provided in advance and is signed by the participant whilst the consenting clinician is present on the telephone. Additional identification questions should be asked, in line with local practice to confirm the identity of the patient prior to the consent form being signed.

If the consent form is completed via videoconference or telephone, the clinician will carry out full consent discussions and answer any questions prior to obtaining agreement from the patient to participate in the study. The clinician will go through each item on the consent form and ask the patient to initial each box, if they agree to consent to the statement, and sign and date the consent form whilst on the call. Consent will be obtained by a suitably-qualified clinician, trained in obtaining consent and delegated that role on the Delegation Log. The patient will be asked to return the signed consent form by post for counter signature by the clinician who obtained consent. The consent form should be received by the clinician who obtained informed consent and counter signed prior to any study-specific activities taking place, this includes randomisation. It is acceptable for a completed consent form to have different dates of signature by the patient and by the person obtaining consent when this is performed remotely.

The participant must personally print their name, sign and date the latest approved version of the Informed Consent Form. In cases where the patient is unable to print their name or date the consent form, for example in cases where patients have Parkinson's disease, this can be completed by another person e.g. a family member, in the presence of the patient at their request. The consent process must be fully documented in the participant's medical notes and in the Event that a participant is assisted to complete the consent form (e.g. to print participant name or date), a file note should be attached to the consent form, detailing that another person has assisted with completion the consent form on behalf of the participant and alongside the reasons why. However, the consent form cannot be signed on behalf of the patient; the patient must always add their own signature.

Participants will be provided with a copy of their fully signed consent form. A copy will be filed in the medical records and a copy sent to the participant's GP along with the PIL. The original signed consent form will be retained at the study site in the Investigator Site File (ISF).

Details of the eligibility assessment and informed consent process should always be documented in the medical records. The original eligibility confirmation document must be signed off by the clinician obtaining informed consent. The original document should be filed in the site file and a copy in the medical records.

A copy of the completed consent form and eligibility confirmation document will also be sent by site to the secure NCTU email ([contact]) – this is for safety monitoring purposes. An nhs.net account must be used to send these documents. For sites that do not have nhs.net accounts, another secure method may be used but this must be discussed with and agreed by the NCTU Trial Manager(s) prior to use.

5.2 Baseline Assessments

The participant's completed consent form must have been received at site and counter-signed by the clinician obtaining remote informed consent before this visit and collection of self-reported assessments can take place. Preference is given to face-to-face appointments, but these can be completed remotely if required. Baseline assessment consists of the Orthostatic Hypotension Questionnaire (OHQ), the EQ-5D-5L or its proxy version [30] and the Nottingham Extended ADL Scale. Also completed will be the Health and Social Service Use questionnaire. Contact details and demographic data including age, sex, ethnicity, height and weight (self-report is acceptable if the assessment is carried out remotely), co-existing medical conditions and culprit medications will be collected.

Supine and nadir standing BP will also be collected at baseline and should be obtained during using one of the methods in section 5.4.1.

In participants with known Parkinson's disease, Dementia with Lewy bodies or Multiple System Atrophy the severity of their motor symptoms will be quantified with parts 1, 2 and 4 of the Movement Disorder Society's Unified Parkinson's Disease Rating Scale (MDS-UPDRS). Online training will be provided to researchers who are unfamiliar with this tool. See Schedule of Events (Section 5.6) for more details.

To be eligible to be randomised, the participant will be required to meet ALL of the inclusion criteria and NONE of the exclusion criteria at this time point (see Section 4)

At all time-points, if participants have remote trial appointments, questionnaires can be posted to them at home, for completion and return to the site.

At the Baseline/Randomisation appointment, participants will be provided with a falls diary to complete at home and requested to bring or post the falls diary prior to/following each follow-up visit.

5.3 Randomisation

Consented participants who meet the eligibility criteria in Section 4 will be randomised on a 1:1:1 ratio to:

- I. Control: Conservative management
- II. Conservative management plus fludrocortisone
- III. Conservative management plus midodrine

Randomisation will be performed by delegated and trained members of the research team at each site using a 24-hour, central, secure, web-based system (Sealed Envelope™). In the event that there are problems with randomisation, the team should contact the NCTU Data Management team during normal working hours who will be able to provide advice. In the event that Sealed Envelope is not available at site due to a technical fault, the team should contact the NCTU who will liaise with Sealed Envelope Support to investigate the cause.

A minimisation algorithm with a random element will be used to assign treatment allocation. Minimisation factors will be by age (≥ 80 or < 80 years), aetiology (neurogenic vs non-neurogenic) and centre (for possible differences in usual care practice). There is an 80% chance the patient is allocated to an arm that minimises imbalance, with 20% chance they are allocated to a different arm.

Participants will be informed of their treatment allocation and the clinical team will provide the advice and relevant medications as per routine practice at the site. IMP should be started as soon as possible. For women of child bearing potential who are randomised to either pharmacological arm of the study, a negative pregnancy test will be required prior to commencing the medication. As part of usual care, a safety blood test will be carried out to monitor urea and electrolytes (both drug arms), and liver function (midodrine arm only). These are safety bloods only and should take place within three months of initiation of the IMP and every six months thereafter. Results will not be recorded for the purpose of the research, unless required for safety reporting in the event of an Adverse Event.

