Exclusion Criteria	
 • OH secondary to acute or reversible causes (e.g. haemorrhage, sepsis) • Use of fludrocortisone or midodrine within the last six months • Terminal illness or life expectancy < 12 months • Supine hypertension (where the risks of treatment outweigh the benefits) at baseline • A known allergy to study medication • A known contra-indication to fludrocortisone or midodrine which outweighs the potential clinical benefit (i.e. if in usual clinical care the clinician and participant feel the risks outweigh the benefits, they would be excluded) • Current or planned pregnancy during the trial period, or breast feeding (If randomised to either pharmacological arm the participant, if female and of child-bearing potential, must have a negative pregnancy test [urine beta-human chorionic gonadotropin (β-hCG)] and are required to use a highly effective contraceptive method during the trial)

	
• Inability to communicate in English• Inability to comply with the study procedures as specified in the schedule of events.• Currently taking part in another clinical trial that would interfere with the outcomes of CONFORM-OH
Intervention & Investigational Medicinal Products	
1. Control: Non-pharmacologic therapy (conservative management)2. Conservative management plus fludrocortisone (50 to 400 mcg tablet(s) daily, titrated according to clinical response)3. Conservative management plus midodrine (2.5 mg BD to 10 mg tablet(s) TDS, titrated according to usual clinical response)

Contents

RESEARCH REFERENCE NUMBERS	2
PROTOCOL APPROVAL SIGNATURE PAGE.....	3
PROTOCOL ACCEPTANCE SIGNATURE PAGE.....	4
KEY TRIAL CONTACTS	5
TRIAL SUMMARY.....	9
Glossary of Abbreviations	16
1. Background and Rationale	19
1.1 Background	19
1.2 Rationale	19
1.3 Commissioned Call.....	20
1.4 Risk Assessment/Evidence of Safety.....	20
2 OBJECTIVES	21
2.1 Primary Objective.....	21
2.2 Secondary Objectives.....	21
2.3 Exploratory Objective.....	21
3. TRIAL DESIGN	21
3.1 Summary of Trial Design	21
3.2 Pilot	22
3.2.1 Pilot Sites.....	22
3.2.2 Progress Criteria.....	22
3.2.3 Progression	23
3.3 Flow Chart of Research Activity	24
3.4 Primary and Secondary Endpoints/Outcome Measures.....	25
3.4.1 Primary Outcome Measure and Endpoint	25
3.4.2 Secondary Outcome Measures and Endpoints.....	25
3.5 Trial Setting and Duration	27

4. Trial Participants	27
4.1 Overall Description of Trial Participants	27

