5.5 Schedule of Events

	Routine Clinical assessment	Consent contact	Clinical review	Clinical review	Clinical review	Clinical review
			Baseline Week 0	Three months	Six months Primary Endpoint	12 months
Follow-up Window	Consent, baseline and randomisation can take place at one visit if the patient receives the PIL in advance			+/- 4 weeks	+/- 6 weeks	+/- 8 weeks
Eligibility Screening	x		x			
Confirm provisional eligibility	x		x			
First approach (treating clinician)	x					
Provide PIL (RN or clinician)	x					
Written informed consent ^a	x	x				
Baseline data collection						
Demographics (DoB, gender, ethnicity) and medical history (including disease duration if PD/MSA/DLB)			x			
MDS-UPDRS parts 1, 2 and 4 (PD / MSA/DLB patients only)			x			
Height and weight			x			
Outcome measures						
Supine and standing BP ^b	x		x	x	x	x
OHQ ^c	x		x	x	x	x
EQ-5D-5L			x	x	x	x
Nottingham Extended ADLs			x	x	x	x
Health and Social Service Use Questionnaire(s)			x	x	x	x
Time and Travel Questionnaire					x	
Randomisation						
Confirm eligibility for randomisation			x			
Randomisation via Sealed Envelope			x			
Routine non pharmacological management – may vary at different sites but might include;						
Lifestyle advice may include: 
 • trigger avoidance • slow, staged, safe standing • salt intake • hydration • bolus water drinking • caffeine intake • education of condition 	x		x	x	x	x
Provide compression garments (if usual clinical practice)	x		x	x	x	x

Physical counter-manoevres (if usual clinical practice)	X		X	X	X	X
Abdominal compression (if usual clinical practice)	X		X	X	X	X
Culprit medication review	X		X	X	X	X
Participants randomised to IMP						
Pregnancy test ^d			X			
Instruction regarding IMP and local prescription arrangements ^e			X	X	X	X
Drug safety monitoring urea & electrolytes as per local practice (drug arms only) ^f			X	X	X	X
Liver function tests (midodrine arm only) as per local practice ^f			X	X	X	X
Confirmation that participant is taking IMP				X	X	X
Additional outcome measures – for all participants						
Provide participant with falls diary			X	X	X	
Falls diary review				X	X	X
Adverse Events review (including hospital admissions)				X	X	X

^a Consent should be obtained at a face-to-face clinic. If this is not possible it can be obtained via videoconference or telephone. Consent only needs to be obtained once (at routine clinical assessment or the consent contact)

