^b If lying and standing blood pressure were measured at the routine clinical assessment they do not need to be repeated at Baseline. For eligibility, BP measurement can be carried out at baseline following consent, or in the preceding eight weeks, or for follow-up visits the preceding six weeks.

^c OHQ to be carried out prior to consent if part of usual care at local site

^d A urine sample pregnancy test for all female participants of child-bearing potential randomised to either intervention arm

^e Fludrocortisone and midodrine will be prescribed and provided according to local clinical practice

^f U&Es and liver function tests to be carried out as per routine practice of treating clinician but at a minimum within three months of initiation of the IMP and every six months thereafter. These will not be reported for research purposes

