6.9.1 Cross-over and Treatment Withdrawal

During the course of the study, the clinical team may consider crossing over of treatment arms, if they judge clinically that a treatment is not working. The same consideration may be made for combination treatments. While we will not seek to dictate clinical decisions, we ask the clinical teams to allow sufficient time (at least four weeks) on maximum tolerated dose, and ideally until the primary outcome is assessed at six months, before considering changing allocated treatment.

If allocated study treatment changes during the trial, details of the changes, including when, by whom and why the decision was made should be recorded in the eCRF.

Participants will not be withdrawn from the trial if treatment contamination, cross-over or withdrawal occurs, but will remain in the trial and be offered all follow-up data collection visits as part of the intention-to-treat analysis.

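### The pregnancy test depends on being randomised to a drug arm, so a control woman who crosses over to a drug has no required test before her first dose

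*Protocol*

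**What the plan says.** The rule appears in five places in the protocol.

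- **Trial Summary, exclusion criteria:** "If randomised to either pharmacological arm the participant, if female and of child-bearing potential, must have a negative pregnancy test".
- **Section 4.3:** the same sentence, "if randomised to either pharmacological arm the participant, if female and of child-bearing potential, must have a negative pregnancy test". It goes on to say that these women are "required to use a highly effective contraceptive method during the trial", so the contraception duty has the same condition.
- **Section 5.3:** for women of child-bearing potential "who are randomised to either pharmacological arm of the study, a negative pregnancy test will be required prior to commencing the medication".
- **Section 5.5, Schedule of Events:** the pregnancy-test row sits under the heading "Participants randomised to IMP" and is marked at Baseline, with nothing at three, six or 12 months.
- **Schedule footnote d:** "A urine sample pregnancy test for all female participants of child-bearing potential randomised to either intervention arm".

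Section 6.9.1 then provides that "the clinical team may consider crossing over of treatment arms, if they judge clinically that a treatment is not working", and extends the same discretion to combination treatment. Teams are asked to "allow sufficient time (at least four weeks) on maximum tolerated dose, and ideally until the primary outcome is assessed at six months", and to record the change in the eCRF. Section 5.4.3 allows for medication changes at reviews between scheduled visits. Neither section mentions a pregnancy test.

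**The concern.** The test protects against exposing a foetus to the drug, so it belongs at the start of the drug. The protocol attaches it to the allocation instead. The two coincide for women randomised to fludrocortisone or midodrine, but not for a control woman of child-bearing potential whose clinician later prescribes one of them.

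The protocol describes the hazard in 7.12: midodrine is not advised in pregnancy, or in women who could become pregnant and are not using contraception, and fludrocortisone carries foetal risk. A control woman who crosses over meets the same hazard without the check that the protocol thought necessary for women allocated to the drug. The issue is participant safety; no estimate or test in the analysis is affected.

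**Working it through.** No power, error-rate or event calculation applies. The check is to read each relevant section against the others and follow two women through the protocol.

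**1. What triggers the test.** Of the five statements listed above, 5 of 5 depend on randomisation to a drug arm and 0 of 5 on first dose whatever the allocation. They are not five independent rules. The Trial Summary copies 4.3, and the Schedule heading and footnote d belong to one row, so there are three sources: 4.3, 5.3 and the Schedule. All three agree.

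**2. When the test is marked.** Baseline: yes. Follow-up visits at three, six and 12 months: 0 of 3.

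**3. Whether control participants can start a drug.** Section 6.9.1 does not exempt control, and the SAP expects such starts:
- Example Table 3 marks the control column as not applicable only for a switch to conservative management, leaving switches to either drug open.
- SAP 4.3 counts prescriptions of each drug irrespective of arm.
- SAP 5.1.2 has a rule for data collected after a participant starts a trial drug she was not allocated.

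**4. Whether any other section requires a test at that point.** Sections 5.4.3, 5.6, 6.9.1, 7.12 and 7.13 were read for this. None does.

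**5. The two women compared.**

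| | Allocated to a drug | Control, later crosses over |
|---|---|---|
| Test required at entry | Yes, before starting the drug | No |
| Test required at the switch | Not applicable | No |
| Required tests before first dose | 1 | 0 |
| Contraception duty under 4.3 triggered | Yes | No |

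**6. How old the entry check would be.** The exclusion of current pregnancy applies to every arm, but it is assessed at entry. Suppose the team follows the ideal in 6.9.1 and waits for the six-month visit. Taking six months as 26 weeks, with the Schedule window of +/- 6 weeks:

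- earliest: 26 - 6 = 20 weeks
- latest: 26 + 6 = 32 weeks

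So the entry check would be 20 to 32 weeks old at first dose. A switch before that visit shortens the interval and a later one lengthens it.

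**The case against.** The strongest reply is that treatment chosen after allocation is usual care by design. Section 6.9.1 declines to dictate clinical decisions, the trial is classed as carrying no more risk than standard care (1.4), and 6.8 sends teams to the BNF for cautions and contra-indications. A prescriber might well test anyway. This stands in part: the missing item is a protocol-mandated check, and silence does not show that no test would be done. But the allocated drugs are also prescribed under local practice, and the protocol still requires a test there. Both drugs are classed as IMP (6.2), crossed-over participants stay in follow-up, and their adverse events are attributed to the treatment received at onset. No reason is given for a lower standard after cross-over.

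Second, other safeguards cover all women. Planned pregnancy during the trial is an exclusion, and that limb looks forward. Section 7.12 excludes women who will not agree to effective contraception, and has the information leaflet tell women to report a pregnancy at once. Section 5.6 names pregnancy as a reason to stop treatment, and 7.13 requires withdrawal and a report within 24 hours. These narrow the gap, and 4.3 and 7.12 can be read together without contradiction: agreement at entry, use on allocation to a drug. None of them is a test, and the reporting and withdrawal steps act only once a pregnancy is known, which may be after exposure.

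Third, few women would be affected. That is accepted.

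**Conclusion.** The gap is real. Followed as written, the protocol requires one negative test before first dose for a woman allocated to a drug and none for a control woman who starts the same drug by cross-over.

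Its reach is probably small. Adults from age 18 are eligible, so women of child-bearing potential can enrol, but section 3.5 expects recruitment mainly from falls, geriatric and movement-disorder settings. The documents give no figure from which to estimate how many would be affected, and none is offered here. The interval of 20 to 32 weeks rests on a switch at the six-month visit and on taking six months as 26 weeks.

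SAP 1.1 records that recruitment was to close early for low numbers, while SAP 2.1 has follow-up continuing to 12 months. A change would therefore help participants still in follow-up and any later trial that reuses this wording. The correction should be made because it is cheap and the hazard is one the protocol itself names.

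**What to change.** Use one trigger that does not depend on the arm: a negative pregnancy test before a participant's first dose of a trial drug (fludrocortisone or midodrine), and highly effective contraception while she takes either. Put it in 4.3 and its Trial Summary copy, in 5.3, and in the Schedule heading and footnote d, and cross-refer to it from 6.9.1 so that a team planning a cross-over sees it. A drug-arm participant already tested before her allocated drug needs no repeat under this rule.

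The cost is a protocol wording amendment, an occasional extra urine test of the kind already used in the drug arms, and a short wait for the result before dosing. Clinicians remain as free to change treatment as they are now.
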